### 4.1 DATA MONITORING COMMITTEE (DMC)

A data monitoring committee for efficacy is not required for this study.

A safety review committee will be established in this study to assess overall safety data and early safety signal in order to protect the ethical and safety interests of the patients recruited into the study, while maintaining, as far as possible, the scientific validity of the study. The SRC is independent of the study team and will comprise of at least one external independent statistician and an external independent physician.

During the study, the SRC will convene at least twice to review the safety and tolerability data after the study recruited the 50th and 100th patient treated for first 8 weeks of treatment phase. Based on the safety information, the SRC has the discretion to make recommendation to the study team based on predefined SRC Charter.

### 4.2 INTERIM ANALYSIS

One interim analysis will take place for this study. The primary analysis of primary endpoint will occur after all patients have the opportunity to complete the 8-week treatment phase study visit. The results will be based on unblinded treatment groups.

Primary comparison:

SHR0302 8mg QD versus placebo, Week 8;  
SHR0302 4mg BD versus placebo, Week 8;  
SHR0302 4mg QD versus placebo, Week 8.

The list of outputs provided with the full set of output templates (planned for the final analysis) will highlight which of these outputs will be provided for the interim analysis.

The [REDACTED] study team, including those responsible for creating the programs to produce the

Document:

\\ieedc-vnasc01\Biosdata\Reistone\SHR0302\CZA55021\Biostatistics

Author:

[REDACTED]

Version Number:

Final v1.2

Version Date:

23Mar2021

Template No: CS\_TP\_BS016 Revision 5  
Effective Date: 01Apr2018

Reference: CS\_WI\_BS005

outputs for the Interim Analysis, will remain blinded. Once the programs have been produced by the [REDACTED] blinded study team in Beijing, these programs will be sent to the [REDACTED] unblinded statistician, who will apply the randomization schedule and provide the Reistone unblinded team with a set of unblinded outputs.

## 4.3 FINAL ANALYSIS

All final, planned analyses identified in this SAP will be performed by [REDACTED] Biostatistics following sponsor authorization of this Statistical Analysis Plan, Database Lock, Sponsor Authorization of Analysis Sets and Unblinding of Treatment.

## 5. ANALYSIS SETS

Agreement and authorization of patients included/ excluded from each analysis set will be conducted prior to the unblinding of the study.

### 5.1 ALL PATIENTS ENROLLED SET [ENR]

The all patients enrolled set will contain all patients who provide informed consent for this study.

### 5.2 ALL PATIENTS RANDOMIZED SET [RND]

The all patients randomized set will contain all patients in the ENR set who were randomized to study medication.

For analyses and displays based on RND, patients will be classified according to randomized treatment.

### 5.3 FULL ANALYSIS SET [FAS]

Full analysis set will comprise of all randomized patients who have received any amount of investigational product (IP) and have observed analysis data in at least one valid Mayo related score. All summaries of baseline and demographic data and all listings will be produced for the FAS population. In the full analysis set, patients will be analyzed according to randomized treatment, regardless of the treatment received.

Document:

\\\ieedc-vnasc01\Biosdata\Reistone\SHR0302\CZA55021\Biostatistics

Author:

[REDACTED]

Version Number:

Final v1.2

Version Date:

23Mar2021

Template No: CS\_TP\_BS016 Revision 5  
Effective Date: 01Apr2018

Reference: CS\_WI\_BS005

## 5.4 PER PROTOCOL ANALYSIS SET [PPS]

Per protocol set is defined as all patients from FAS who have week 8 efficacy data and do not have significant protocol violation.

## 5.5 SAFETY ANALYSIS SET [SS]

The Safety analysis set will comprise all patients who received any amount of investigational product and will be based on the actual treatment received, if this differs from that to which the patient was randomized to. The Safety analysis set will be used for all summaries of safety data.

If there is any doubt whether a patient was treated or not, they will be assumed treated for the purposes of analysis.

## 6. GENERAL CONSIDERATIONS

### 6.1 REFERENCE START DATE AND STUDY DAY

Study Day will be calculated from the reference start date and will be used to show start/ stop day of assessments and events.

Reference start date is defined as the day of the first dose of investigational product (Day 0 is the day of the first dose of investigational product) and Study Day will appear in every listing where an assessment date or event date appears.

- If the date of the event is on or after the reference date, then:  
Study Day = (date of event – reference date).
- If the date of the event is prior to the reference date, then:  
Study Day = (date of event – reference date).

In the situation where the event date is partial or missing, Study Day, and any corresponding durations will appear partial or missing in the listings.

---

Document:

\\\ieedc-vnasc01\Biosdata\Reistone\SHR0302\CZA55021\Biostatistics

Author:

[REDACTED]

Version Number:

Final v1.2

Version Date:

23Mar2021

Template No: CS\_TP\_BS016 Revision 5  
Effective Date: 01Apr2018

Reference: CS\_WI\_BS005

## 6.2 BASELINE

Unless otherwise specified, baseline is defined as the last non-missing measurement (including unscheduled assessments) taken prior to first dose on or before Day 0. In the case where the last non-missing measurement and the reference start date coincide, that measurement will be considered pre-baseline. However, Adverse Events (AEs) and medications commencing on the first dose date will be considered as post-baseline. For the related assessments such as systolic blood pressure (SBP) and diastolic blood pressure (DBP), it is desirable that both baseline values come from the same measurement and not from different dates/visits in case one value is missing.

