## 6.7 COMMON CALCULATIONS

- For quantitative measurements, change from baseline will be calculated as:  
Change from baseline =Test Value at Visit X – Baseline Value
- For quantitative measurements, percent change from baseline will be calculated as:  
Percent change from baseline=  $((\text{Test Value at Visit X} - \text{Baseline Value}) / \text{Baseline Value}) * 100$

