### **16.1.1 All TEAEs**

An overall summary of TEAEs in treatment phase will be provided. The number and percentage of patients experiencing AEs and the number of TEAEs will be tabulated.

Incidence of TEAEs will be presented by System Organ Class (SOC) and Preferred Term (PT) and summarized in treatment phase for each SHR0302 dose level , placebo and overall.

All TEAEs during the whole study period will also be summarized for the following groups similarly.

- 8 mg QD total: 8mg QD during the whole study period+ Placebo->8mg QD group after treatment phase
- 4 mg BD total: 4 mg BD during the whole study period + Placebo->4mg BD group after treatment phase
- 4 mg QD total: 4 mg QD during the whole study period + Placebo->4mg QD group after treatment phase
- Placebo only: Placebo group during treatment phase

Incidence of TEAEs will also be broken down further as shown in the following sections.

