### 16.3 LABORATORY EVALUATIONS

Results from the central laboratory will be included in the reporting of this study for Hematology, Chemistry, Urinalysis and Others. All laboratory assessments will be listed in the outputs.

Presentations will use SI Units. All laboratory data will be summarized and listed for all patients in the SS set by visits where data are collected.

Quantitative laboratory measurements reported as “< X”, i.e. below the lower limit of quantification (BLQ), or “> X”, i.e. above the upper limit of quantification (ULQ), will be converted to X for the purpose of quantitative summaries, but will be presented as recorded, i.e. as “< X” or “> X” in the listings.

Quantitative laboratory measurements will be compared with the relevant laboratory reference ranges in SI units and categorized as:

- Low: Below the lower limit of the laboratory reference range.
- Normal: Within the laboratory reference range (upper and lower limit included).
- High: Above the upper limit of the laboratory reference range.

The following summaries will be provided for laboratory data:

- Actual and change from baseline by visit (for quantitative measurements)
- Incidence of abnormal values according to normal range criteria
- Shift tables representing categorical change of laboratory evaluation results from baseline to each post baseline
- Listing of patients with laboratory results

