#### 16.4.1 ECG MARKEDLY ABNORMAL CRITERIA

For all patients in the safety analysis population, the maximum QTcF interval will be summarized using frequency tables for each SHR0302 dose level, placebo and overall in treatment phase for values of clinical importance using the range criteria below.

- Absolute values for post baseline QTcF interval will be classified as:

Cumulative Category:

- ≤ 450 msec
- > 450 msec
- > 480 msec
- > 500 msec

Interval Category:

- ≤ 450 msec
- > 450 to ≤ 480 msec
- > 480 to ≤ 500 msec
- > 500 msec

- Change from Baseline for QTcF interval will be classified as:

Cumulative Category:

- <0 msec increase from baseline
- ≥ 0 msec increase from baseline
- >30 msec increase from baseline
- >60 msec increase from baseline

Interval Category:

- <0 msec increase from baseline
- ≥ 0 to ≤ 30 msec increase from baseline
- > 30 to ≤ 60 msec increase from baseline
- >60 msec increase from baseline

The maximum QTcF interval will also be summarized similarly for 8 mg QD total, 4 mg BD total, 4 mg QD total, Placebo only and overall during the whole study period.

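### In the QTcF change-from-baseline table, placebo patients who switch to SHR0302 are pooled into the dose-total columns but measured from Day 0, before they took placebo

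*SAP*

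**What the plan says.** **Baseline.** SAP 6.2 gives a default that holds unless another is specified: "baseline is defined as the last non-missing measurement (including unscheduled assessments) taken prior to first dose on or before Day 0". SAP 6.1 anchors Day 0: "Reference start date is defined as the day of the first dose of investigational product". In the placebo arm the first investigational product is placebo. SAP 6.7 defines change against that single value: "Change from baseline =Test Value at Visit X – Baseline Value". Neither document gives a second baseline for patients who switch.

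**Pooling.** SAP 16.1.1 builds the whole-study columns in this way: "8 mg QD total: 8mg QD during the whole study period+ Placebo->8mg QD group after treatment phase", with the same pattern for the other two doses. SAP 16.4.1 applies those columns to QTcF: "The maximum QTcF interval will also be summarized similarly for 8 mg QD total, 4 mg BD total, 4 mg QD total, Placebo only". The same section contains the change table ("Change from Baseline for QTcF interval will be classified as"), with cut-points at 0, 30 and 60 msec.

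**Other safety tables.** SAP 16.3 plans "Shift tables representing categorical change of laboratory evaluation results from baseline to each post baseline", along with changes by visit. SAP 16.5 plans vital-sign changes by visit, and the markedly abnormal criteria in 16.5.1 also use change from baseline. None of these sections names its treatment columns. Appendix 1 keeps the dose-total columns for certain TEAE and ECG tables and otherwise lists three separate Placebo->dose groups. Protocol 9.3.4.4 instead groups laboratory, vital-sign and ECG summaries by the treatment being taken at each visit. SAP 3.3 records no departure from the protocol on this.

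**The concern.** In a dose-total column the reader expects a change to mean a change since the patient was last off SHR0302. That is true of patients randomised to a dose. For a switcher the reference value is 8 weeks too early, so the tabulated change is the sum of what happened on placebo and what happened on drug. Colitis activity and concomitant treatment can both move over those 8 weeks.

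The switch also offers a within-patient comparison before and after drug, which a Day 0 reference blurs. SAP 3.1 says the study is meant to support the choice of one or two doses, so dose-level safety columns will be read with that in mind.

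**Working it through.** The plan states no figure on this point. The inputs are the sample size, the allocation ratios and the dropout rate.

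**1. How many patients are affected**

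- Randomised: 152, allocated 1:1:1:1 (protocol 1.3), so 152/4 = 38 per arm.
- Placebo patients are pre-assigned 1:1:1 to the three doses (protocol 1.3), so 38/3 = 12.67 per dose.
- Share of a dose-total column if every placebo patient enters the extension: 12.67/(38 + 12.67) = 12.67/50.67 = 25%.
- With the planned 8% dropout (protocol 9.2.1) and every completer entering: 38 × 0.92/3 = 11.65, and 11.65/49.65 = 23.5%.
- With assumed uptake of 80%: 10.13/48.13 = 21.1%. With 60%: 7.6/45.6 = 16.7%.
- One switcher in a different category moves a full-uptake column by 1/50.67 = 2.0 percentage points.

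**2. When the category changes**

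Let d be the shift that arose on placebo and persists, and e the change after the switch. Day 0 gives d + e; a pre-switch baseline gives e. The category differs only when the two fall on opposite sides of a cut-point. With d = +10 msec, any e above 20 and up to 30 is counted as more than 30. With d = −10 msec, any e above 30 and up to 40 is not. With d = 0 the expected results are the same.

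Persistence is required because switchers enter the dose-total columns only after the treatment phase. Their post-switch ECGs are at Weeks 9, 16 and 18, with none at Week 12 (protocol 5.12).

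**3. Illustration under assumptions**

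The documents give neither a visit-to-visit SD for QTcF nor any drift on placebo. Both are assumed here. One million patients were simulated per setting with no drug effect, independent visit noise, and the larger of two post-switch values (Weeks 9 and 16). The table shows the percentage of switchers with an increase above 30 msec.

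| Visit SD (msec) | Day 0, d = 0 | Day 0, d = 5 | Day 0, d = 10 | Day 0, d = 15 | Week 8, any d |
|---|---|---|---|---|---|
| 8 | 0.8 | 2.6 | 6.8 | 15.6 | 0.7 to 0.8 |
| 10 | 3.1 | 6.9 | 13.4 | 23.4 | 3.1 |
| 15 | 13.5 | 19.7 | 27.5 | 36.6 | 13.4 |

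At SD 10 and d = 10, the expected number above 30 msec among 12.67 switchers is 1.70 with Day 0 and 0.40 with Week 8. The difference of 1.30 in a column of 50.67 is 2.6 points. At SD 8 it is (0.86 − 0.09)/50.67 = 1.5 points, and at SD 15 it is (3.49 − 1.70)/50.67 = 3.5 points. These figures show how the mechanism works; they do not estimate what happens in this trial.

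**4. Is a pre-switch value available?**

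Protocol 5.12 schedules ECG, haematology, chemistry, lipids and vital signs at Week 8. However, protocol 6.1.2 has a morning dose taken in the clinic at that visit, and the visible text does not say that the ECG and sampling come before the first extension dose. The SAP has no rule assigning the Week 8 ECG to a phase. Its only phase algorithm, for TEAE onset in Appendix 2, puts the Week 8 visit date in the extension. If that cut were reused for ECGs, a value recorded on placebo would itself be counted under a dose.

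**The case against.** The strongest reply is that little of the safety output is touched, and much of it stands.

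- **Laboratory and vital signs.** A reader might infer that these changes are charged to a dose in the same way. The SAP does not say so. Under Appendix 1 switchers sit in their own Placebo->dose columns by visit, where a shift on placebo is already visible at Week 8. Misattribution follows only if the protocol 9.3.4.4 grouping governs.
- **The 60 msec category.** A reader might infer that a placebo patient with a rise above 60 msec is later counted under a dose. Protocol 5.9 withdraws such a patient, and protocol 1.3 bars those withdrawn early in the treatment phase from the extension. What remains exposed is the 30 msec cut-point, and a total above 60 msec reached by adding a rise on placebo to a rise on drug.
- **Unaffected outputs.** The treatment-phase QTcF table, the absolute QTcF categories and the laboratory incidences by reference range do not depend on the switchers' baseline. Safety analysis is descriptive (SAP 16).
- **Two references in one column.** This is a real cost. If the withdrawal rule in protocol 5.9 uses the Day 0 value, counts above 60 msec for switchers would no longer match it exactly.
- **Templates.** SAP 8 refers to output templates that are not in the documents. They could specify a second baseline, but a baseline definition belongs in the SAP text.

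None of this removes the QTcF point, which follows from rules the SAP states.

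**Conclusion.** The point holds for the QTcF change-from-baseline categories in the three dose-total columns. A single Day 0 baseline combined with the stated pooling means that up to 25% of each column is measured from 8 weeks before any SHR0302. The share is 23.5% with the planned dropout and full uptake by completers, and 16.7% at 60% uptake. The error can run in either direction, and it needs a placebo-phase change that persists after the switch.

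The documents support no estimate of bias. The 1.5 to 3.5 point range applies to an assumed persistent 10 msec shift and SDs of 8 to 15 msec, and with no shift there is no expected difference. For laboratory, by-visit ECG and vital-sign changes the finding is a conflict between protocol 9.3.4.4 and SAP Appendix 1, not an established misattribution. The change should be made because these columns inform dose selection and the remedy is cheap, but it does not threaten the randomised comparison.

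**What to change.** 1. In SAP 6.2 and 16.4.1, state that for patients randomised to placebo the QTcF change categories in the dose-total columns use the last non-missing value before the first extension dose. This will normally be Week 8, once confirmed as taken before that dose. Count values up to and including it under placebo.
2. Keep the Day 0 baseline for treatment-phase tables and for patients randomised to a dose. Footnote the two baselines.
3. Reconcile protocol 9.3.4.4 with the separate Placebo->dose columns in SAP Appendix 1 for laboratory, by-visit ECG and vital-sign change tables. If switchers are to appear under a dose after Week 8, use the same pre-switch baseline for them and record the decision in SAP 3.3.
4. In the same edit, correct the 4mg QD total row in Appendix 1. It names the Placebo->4mg BD group, whereas SAP 16.1.1 names Placebo->4mg QD.

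The cost is a few sentences, one extra baseline flag and a footnote. No new data are needed, provided the timing of the Week 8 ECG relative to the first extension dose can be confirmed.

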## 6.3 DERIVED TIMEPOINTS

For some endpoints, Last-observation-carried-forward (LOCF) or Baseline-observation-carried-forward (BOCF) approach will be applied for subscore other than endoscopy of Mayo score. In the by-visit summary, “LOCF imputation” or “BOCF imputation” will be used to make it clear what is being shown in the outputs.

## 6.4 UNSCHEDULED VISITS, RETESTS AND EARLY TERMINATION DATA

In general, for by-visit summaries, data recorded at the nominal visit will be presented. Unscheduled measurements will not be included in by-visit summaries but will contribute best/ worst case value where required .

In the case of a retest (same visit number assigned), the latest available measurement for that visit will be used for by-visit summaries.

Listings will include scheduled, unscheduled, retest and early discontinuation data.

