- Perform liver event follow up assessments, and monitor the subject until liver chemistries resolve, stabilize, or return to baseline values as described below.
- Withdraw the subject from the **study** (unless further safety follow up is required) after completion of the liver chemistry monitoring as described below.
- Do not re-challenge with investigational product.

In addition, for criterion 1:

- Make every reasonable attempt to have subjects return to clinic within **24 hours** for repeat liver chemistries, liver event follow-up assessments (see below), and close monitoring.
- A specialist or hepatology consultation is recommended.

- Monitor subjects twice weekly until liver chemistries (ALT, AST, alkaline phosphatase, bilirubin) resolve, stabilise or return to within baseline values

For criteria 2, 3, 4 and 5:

- Make every reasonable attempt to have subjects return to clinic **within 24-72 hrs** for repeat liver chemistries and liver event follow up assessments (see below)
- Monitor subjects weekly until liver chemistries (ALT, AST, alkaline phosphatase, bilirubin) resolve, stabilize or return to within baseline values; criterion 5 subjects should be monitored as frequently as possible.

Subjects with $\text{ALT} \geq 3 \times \text{ULN}$ **but** $< 5 \times \text{ULN}$ **and** bilirubin $< 2 \times \text{ULN}$, without hepatitis symptoms or rash, and who can be monitored weekly for 4 weeks:

- Notify the Reistone/designated CRO medical monitor within 24 hours of learning of the abnormality to discuss subject safety.
- Can continue investigational product.
- Must return weekly for repeat liver chemistries (ALT, AST, alkaline phosphatase, bilirubin) until they resolve, stabilise or return to within baseline.
- If at any time these subjects meet the liver chemistry stopping criteria, proceed as described above.
- If, after 4 weeks of monitoring, $\text{ALT} < 3 \times \text{ULN}$ and bilirubin $< 2 \times \text{ULN}$, monitor subjects twice monthly until liver chemistries normalize or return to within baseline values.

For criteria 1-5, make every attempt to carry out the **liver event follow up assessments** described below:

- Viral hepatitis serology including:
 - Hepatitis A IgM antibody;
 - Hepatitis B surface antigen and Hepatitis B Core Antibody (IgM);
 - Hepatitis C RNA;
 - Cytomegalovirus IgM antibody;
 - Epstein-Barr viral capsid antigen IgM antibody (or if unavailable, obtain heterophile antibody or monospot testing);

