## 6.5 WINDOWING CONVENTIONS

No visit windowing will be performed in the statistics for this study.

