## 16.7 OTHER SAFETY ASSESSMENTS

Female patients of childbearing potential will be tested for serum beta-human chorionic gonadotropin ( $\beta$ -hCG) at screening visit. In addition, urine  $\beta$ -hCG test will be done at baseline and at each study visit until the end of follow-up period. If at any point there is a case of a positive urine  $\beta$ -hCG test, and this is confirmed by serum  $\beta$ -hCG, the patient will be withdrawn from the study and all the necessary follow up will be conducted. Urine pregnancy test will be done in females of childbearing potential only. Pregnancy tests data will be listed.

Phase II liver chemistry stopping and follow up criteria have been designed to assure patient safety and evaluate liver event etiology (in alignment with the FDA premarketing clinical liver safety guidance). Please refer to section 7.3.9 of the protocol for details. Liver Event Follow up Assessments and Liver Event Alcohol intake will be listed.

Supplemental lab data will be listed

Microscopy data, if available, will be listed.

A listing will be provided for patients whose trial participation are impacted by COVID-19, including patient number and site number together with a description of the impact. These protocol deviations are documented in [REDACTED] management system.

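### Laboratory tables can understate transient or severe abnormalities: same-visit retests overwrite, unscheduled values are left out, and no worst-value or threshold table is specified

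*SAP*

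**What the plan says.** SAP 6.4 sets two rules for by-visit summaries. For repeats under one visit number: "In the case of a retest (same visit number assigned), the latest available measurement for that visit will be used for by-visit summaries". For everything off schedule: "Unscheduled measurements will not be included in by-visit summaries but will contribute best/ worst case value where required". The same section keeps all values in listings: "Listings will include scheduled, unscheduled, retest and early discontinuation data". SAP 6.5 adds "No visit windowing will be performed in the statistics for this study", so the recorded visit label alone decides which rule applies to a repeat.

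SAP 16.3 puts laboratory data on a visit basis: "All laboratory data will be summarized and listed for all patients in the SS set by visits where data are collected". It asks for actual values and change by visit, incidence outside the normal range, and "Shift tables representing categorical change of laboratory evaluation results from baseline to each post baseline". Results are classed only as Low, Normal or High. Other safety domains get more: SAP 16.4.1 tabulates each patient's maximum QTcF in bands, and SAP 16.5.1 sets limits for markedly abnormal vital signs.

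The protocol orders repeats because a value is abnormal. Under Protocol 7.3.9, study drug is withdrawn when a liver stopping criterion is met, and the subject is recalled within 24 hours or 24-72 hours, then monitored twice weekly or weekly. For lesser ALT rises without symptoms: "Must return weekly for repeat liver chemistries (ALT, AST, alkaline phosphatase, bilirubin) until they resolve, stabilise or return to within baseline". SAP 16.7 says of the associated work-up: "Liver Event Follow up Assessments and Liver Event Alcohol intake will be listed".

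**The concern.** Safety retests are not a random sample of results. They are mostly triggered by an abnormal value and, for the liver stopping criteria, follow withdrawal of study drug. Taking the latest value of a visit then favours the later, possibly recovered one. Leaving out unscheduled draws can miss a peak that occurs between visits. A worst-post-baseline table would recover both, but none is specified for laboratory data, so the worst-case clause in SAP 6.4 has nothing in SAP 16.3 to act on.

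A second gap does not depend on visit labels. Three categories cannot grade severity. ALT just above the upper limit and ALT at or above 5xULN are both High. A subject whose baseline haemoglobin is already below the laboratory's lower limit (Protocol 5.3 admits values down to 9.0 g/dL) and who falls below the 7.0 g/dL value in Protocol 5.9 appears as Low to Low.

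This matters because Protocol 1.1 names anaemia and thrombocytopenia as concerns linked to JAK2 inhibition, and SAP 3.1 says the trial's efficacy and safety data are to support selection of one or two doses. Per-arm rates of these laboratory events are a natural input to that choice.

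**Working it through.** The documents state no figure on this point, so there is none to reproduce. The check traces the rules and then sizes one of the two routes under stated assumptions.

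**Step 1: follow one repeat.** Suppose ALT is abnormal at Week 4.

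- Repeat labelled Week 4: the Week 4 table shows the repeat. If it is normal, the abnormal value leaves the table.
- Repeat labelled unscheduled: the repeat is dropped and the abnormal Week 4 value stays. Something is lost only if the repeat is a higher peak, or if an unscheduled draw is the first to show an abnormality.

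One repeat cannot do both. SAP Appendix 1 has a separate Unscheduled Visit label, but neither document says which label a protocol-ordered repeat receives. A recall at 24-72 hours could plausibly keep the visit number; weekly monitoring more plausibly would not.

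**Step 2: where peaks can fall.** The Time and Event Table (Protocol 5.12) has chemistry and haematology after baseline at Weeks 1, 4, 8, 9, 12, 16 and 18. Four weekly repeats after a Week 4 signal fall at Weeks 5, 6, 7 and 8; the first three lie between visits. If they are labelled unscheduled, an ALT that first reaches 5xULN at one of them enters no laboratory table that SAP 16.3 specifies.

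**Step 3: size of the overwriting route.** Inputs: 152/4 = 38 patients per arm (sample size in SAP 3.1); k patients abnormal at a visit, each repeated once; s = share of repeats filed under the same visit number; q = share of repeats that are normal. The values of k, s and q are assumed. Expected rate shown = k(1 - s x q)/38.

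| k | Observed at visit | s | q = 0.25 | q = 0.50 | q = 0.75 |
|---|---|---|---|---|---|
| 2 | 5.3% | 0 | 5.3% | 5.3% | 5.3% |
| 2 | 5.3% | 0.5 | 4.6% | 3.9% | 3.3% |
| 2 | 5.3% | 1 | 3.9% | 2.6% | 1.3% |
| 4 | 10.5% | 0 | 10.5% | 10.5% | 10.5% |
| 4 | 10.5% | 0.5 | 9.2% | 7.9% | 6.6% |
| 4 | 10.5% | 1 | 7.9% | 5.3% | 2.6% |

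Example: 4 x (1 - 1 x 0.75)/38 = 1/38 = 2.6%. With k = 2, s = 1 and independent repeats, the chance that both abnormal values disappear is q squared: 6%, 25% and 56% for the three values of q.

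A worst-post-baseline table would count all k patients whatever s and q are: 2/38 = 5.3% or 4/38 = 10.5%. The other route, peaks seen only off schedule, cannot be sized from the documents.

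**The case against.** The strongest reply is that the signal survives elsewhere. Every value stays in the listings. SAP 8 gives minimum and maximum for continuous variables. An abnormal laboratory result can be an adverse event (Protocol 7.3.12). Hy's Law cases are SAEs by definition and are tabulated (SAP 16.1.4), as are TEAEs leading to discontinuation (SAP 16.1.3). An independent safety committee reviews data at least twice (SAP 4.1). All of this stands, so it would be wrong to infer that liver events are only listed; SAP 16.7 concerns the follow-up work-up and alcohol intake. But listings give no rate per arm. The by-visit minimum and maximum are taken after the SAP 6.4 rules have applied, and they do not count subjects. Isolated ALT rises or cytopenias reach the adverse-event tables only if reported as events.

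Two limits on the text also stand. The output templates mentioned in SAP 8 are not among the documents. The incidence item in SAP 16.3 is not itself marked as by visit, so the worst-case clause might be meant to apply there; the section's general by-visit wording points the other way.

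A reader might infer more than the documents support:

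- That ordered repeats generally remove toxicity signals. An unscheduled repeat leaves the abnormal scheduled value in place.
- That four-week thyroid rechecks fall outside visits. Thyroid tests are scheduled at every visit, and rechecks from baseline or Weeks 4, 8 or 12 land on Weeks 4, 8, 12 or 16.
- That test-retest regression to the mean measures the loss. Such a calculation describes drug-free values just beyond a reference limit and assumes every repeat keeps its visit number.
- That drug-placebo differences must shrink. Persistent drug effects are less likely to normalise on repeat than chance values, so the effect on the contrast is not determined.

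**Conclusion.** The point holds in conditional form. On the text, the SAP lets a same-visit retest replace an abnormal laboratory value, leaves unscheduled values out of by-visit tables, and specifies no laboratory table that would recover either. The loss of scheduled abnormal values ranges from nil, if all repeats are unscheduled, to a fall from 10.5% to between 7.9% and 2.6% in the example with 4 of 38 abnormal, all repeats same-visit and 25% to 75% normalising. Those shares are assumptions. Missed off-schedule peaks would come on top and cannot be quantified here.

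The severity gap is firmer because visit numbering does not affect it: no laboratory table described in SAP 16.3 counts subjects meeting the laboratory criteria in Protocol 5.9 or 7.3.9. The plan should be changed on both counts. The efficacy analyses are not affected.

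**What to change.** In SAP 6.4 and 16.3:

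1. For safety laboratory data, keep the valid scheduled value in by-visit summaries and use a retest only when the scheduled sample was invalid. State how protocol-ordered repeats are assigned to visits.
2. Add abnormality and shift tables based on each subject's worst post-baseline value per study phase, drawing on scheduled, unscheduled, retest and early-withdrawal data.
3. In that table, count subjects by arm who reach the laboratory thresholds already in Protocol 5.9 (haemoglobin, neutrophils, platelets, lymphocytes, leukocytes) and 7.3.9 (ALT at or above 3x and 5xULN; ALT at or above 3xULN with bilirubin at or above 2xULN). Absolute lymphocytes must be derived from the white cell count and the percentage, since Protocol Table 3 lists only those two.

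The cost is some SAP wording and one or two more tables from data already collected. The downside is that a worst-value table can pick up an occasional spurious result; the listings allow such a value to be checked.
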